5.1 PRIMARY ENDPOINTS

The primary endpoint in this study is the change from baseline in HbA_{1c} (%) at week 24. HbA_{1c} will additionally be analysed in mmol/mol.

5.2 SECONDARY ENDPOINTS

5.2.1 Key secondary endpoint(s)

Key secondary endpoints of this study are:

[figure not shown]
- Mean 24-hour ambulatory SBP (mmHg): Change from baseline at week 12
- Mean trough ambulatory SBP (mmHg): Change from baseline at week 12
- Body weight (kg): Change from baseline at week 24
- Trough seated SBP (mmHg): Change from baseline at week 12

[figure not shown]
5.2.2 (Other) Secondary endpoint(s)

[figure not shown]
Other secondary endpoints of this study are:

- Change from baseline in mean 24-hour ambulatory SBP (mmHg) at week 24
- Change from baseline in mean 24-hour ambulatory DBP (mmHg) at week 12

- Change from baseline in mean 24-hour ambulatory DBP (mmHg) at week 24
- Change from baseline in trough seated SBP (mmHg) at week 24
- Change from baseline in trough seated DBP (mmHg) at week 12
- Change from baseline in trough seated DBP (mmHg) at week 24

6 GENERAL ANALYSIS DEFINITIONS

6.1 TREATMENT(S)

There will be 5 treatment study phases in this trial: screening, placebo run-in, study treatment phase (with either empagliflozin, matching placebo), post-treatment and post-study.

Table 6.1: 1 Treatment regimens / study intervals

Label	Interval	Start date	Start time
Screening	Screening period	Date of informed consent	00:00
Run-in	Run-in	Date of first administration of run-in medication	00:00
Placebo Empagliflozin	Double-blind treatment period	Date of first administration of double-blind study medication	Time of first administration of double-blind study medication, 12:00 if missing
Post-treatment	Post-treatment	Date of last intake of trial drug + X* +1 day	00:00
Post-study	Post-study	Last contact date +1 day	00:00

* The endpoint specific follow-up periods for the assignment to active treatment are presented in detail in [Section 6.7](#). This is relevant for the statistical programming team only.

The purpose of the definitions above is to describe all the different study/treatment intervals, in which a patient can be assigned during the course of the trial. Note that the term “treatment regimen” can also cover time periods with no active treatment.

The endpoint-specific follow-up periods for the assignment to active treatment are presented in detail in Section 6.7.

The efficacy analyses will follow the intention-to-treat (ITT) principle in assigning patients to treatment groups, i.e. patients will be analysed as randomised.

Safety analyses will assign patients to the treatment group as treated. If a patient erroneously receives the wrong trial drug, the patient will be analysed as per the first treatment received. Drug-related AEs are analysed according to actual medication taken. Actual medication taken refers to medication at onset of AE. In addition, AEs with an onset during the time of the incorrect study treatment will be listed separately.

6.2 IMPORTANT PROTOCOL VIOLATIONS

Not all important protocol violations (iPVs) will generate exclusion from the per protocol set (PPS). Violations that lead to exclusion from analysis populations are indicated as such in [Table 6.2: 1](#).

iPV definitions will include consideration of, among others, important violations of entry criteria, treatment non-compliance, treatment dispensing errors, prohibited concomitant medication and premature unblinding.

Table 6.2: 1 List of important protocol violations

PV Category/ Code	Description	(Comments)	Criterion to check for PV	Exclusion from	
A	Entrance criteria not met				
A1	Target indication not met				
	A1.01	No type 2 diabetes	Inclusion criterion checked	I1	PPS
A2	Inclusion criteria not met				
	A2.01	HbA _{1c} out of range	HbA _{1c} out of range for inclusion (see individual inclusion criterion) by >0.2% i.e. inclusion only if value is in [7.3-11.2%] interval	I3, for Protocol Version 4 the range has changed (>=7.0 % instead of 7.5% so values within [6.8-11.2%]) will be included from Protocol Version 4 onwards	PPS
	A2.02	Age out of range (at V1)	See individual inclusion criterion	I7	None
A3	Exclusion criteria violated				
	A3.01	Uncontrolled FPG level	Exclusion criterion checked	E1	None
	A3.02	Additional anti-diabetic background therapy	Exclusion criterion checked	E2 (different definitions for Protocol Version 1+2 compared to Protocol Version 3 [with regards to background therapy])	PPS

Table 6.2: 1 List of important protocol violations (cont.)

PV Category/ Code		Description	(Comments)	Criterion to check for PV	Exclusion from
	A3.03	Relevant concomitant diagnoses	Exclusion criterion checked or see individual exclusion criterion	E8, E9, E10, E11, E15, E17	None
	A3.04	Bariatric or other relevant and other gastrointestinal surgery within the last two years	Exclusion criterion checked	E14	PPS
	A3.05	Blood dyscrasias or any disorders causing hemolysis or unstable red blood cell count	Exclusion criterion checked	E16	PPS
	A3.06	Indication of liver disease	Exclusion criterion checked	E12 + data check for any issues ¹	None
	A3.07				
	A3.08	Treatment with protocol excluded antiobesity drugs	Exclusion criterion checked or Treatment with anti-obesity drugs 3 months prior to informed consent or any other treatment at the time of screening (i.e. surgery, aggressive diet regimen, etc.)	E18 (protocol version 2), E19 (protocol version 1)	PPS
	A3.09	Renal insufficiency or renal impairment (assessed by eGFR)	Exclusion criterion checked	E13 + data check for any issues ¹	PPS

Table 6.2: 1 List of important protocol violations (cont.)

PV Category/ Code		Description	(Comments)	Criterion to check for PV	Exclusion from
	A3.10	Treatment with protocol excluded systemic steroids or recent change in thyroid hormone dose	Exclusion criterion checked or current treatment with systemic steroids at time of informed consent or change in dosage of thyroid hormones within 6 weeks prior to informed consent or any other uncontrolled endocrine disorder except T2DM. (Treatment with local and inhaled steroids is allowed)	E19 (protocol version 2), E20 (protocol version 1)	PPS
	A3.11	Intake of an investigational drug within 30 days prior to intake of study medication in this trial	Exclusion criterion checked (Medical judgment), depending on the type of drug given in the prior trial (only if investigational drug interferes with glucose metabolism).	E22 (protocol version 2), E23 (protocol version 1)	PPS Final decision at DBL meeting
	A3.12	Specific exclusion criterion for premenopausal women violated	Exclusion criterion checked	E20 (protocol version 2), E21 (protocol version 1)	None

Table 6.2: 1 List of important protocol violations (cont.)

PV Category/ Code		Description	(Comments)	Criterion to check for PV	Exclusion from
	A3.13	Relevant alcohol or drug abuse and other conditions affecting study compliance	Exclusion criterion checked	E21 (protocol version 2), E22 (protocol version 1)	None
	A3.14	Any other clinical condition unsafe for participation that would jeopardise patient safety while participating in this clinical trial	Exclusion criterion checked	E23 (protocol version 2), E24 (protocol version 1)	None
	A3.17	Diagnosis of autoimmune diabetes	As defined in protocol	E7	None
B	Informed consent				
	B1	Informed consent not available	Date of informed consent missing or No signature on patient's "Declaration of Informed Consent". Patient's data will not be used at all.	I8 ¹ data check or manual	All
	B2	Informed consent too late	Date of informed consent not obtained prior to any study related procedure. Minimum requirement \leq date of Visit 1/date of any study procedure	I8 ¹ data check or manual	None
C	Trial medication and randomisation				
C1	Incorrect trial medication taken				

Table 6.2: 1 List of important protocol violations (cont.)

PV Category/ Code		Description	(Comments)	Criterion to check for PV	Exclusion from
	C1.01	No study medication taken	Patient randomised but no study medication taken	¹	TS, FAS, PPS
	C1.02	Incorrect trial medication taken	Wrong medication taken for more than 20% of the overall treatment duration or for more than 20% of the last visit interval before the primary endpoint assessment (different medication than the patient was randomized to taken i.e. drug kit recorded in eCRF from different treatment group than drug kit assigned by IVRS) [manual check PV].	Can only be finally judged after DBL since unblinding information is required. ¹	PPS
C2	Randomisation not followed				
	C2.01	Treated without randomisation	Patient treated according to eCRF, but not randomised according to IVRS.		PPS
	C2.02	Randomization without successful completion of baseline ABPM	Patient randomized without successful completion of baseline ABPM with a mean SBP 135-175 mmHg as required.	I5	None
C3	Non-compliance				

Table 6.2: 1 List of important protocol violations (cont.)

PV Category/ Code		Description	(Comments)	Criterion to check for PV	Exclusion from
	C3.01	Non-compliance with trial drug intake	Overall study treatment compliance outside 80% and 120% (inclusive) or study treatment compliance below 80% in the last visit interval before primary endpoint assessment. Overall compliance will be calculated as a weighted average of reported compliance. The weighted sum of all reported compliance over the actual visits will be divided by the total duration until visit where all medication is returned.	¹	PPS
	C3.03	Last treatment more than 7days prior to next visit	Last treatment more than 7 days prior to next visit.	¹	PPS
C4	Medication code broken				
	C4.01	Medication code broke without just cause	Medication code was broken for no valid reason. Final decision at the DBL meeting based on medical judgment.		PPS Final Decision at DBL Meeting
D1	Concomitant medication				
D2	Prohibited medication use				

Table 6.2: 1 List of important protocol violations (cont.)

PV Category/ Code	Description	(Comments)	Criterion to check for PV	Exclusion from
	D2.01	Use of prohibited medication during treatment period	Review of eCRF for prohibited medication. Final decision at the DBL meeting based on medical judgment.	PPS Final Decision at DBL Meeting
D3	Mandatory medication not taken			
	D3.01	Background antidiabetic therapy not taken as specified in the protocol	Antidiabetic background therapy dose changed.	PPS
E	Missing data			
	E.01	No baseline HbA _{1c} value	No valid baseline HbA _{1c} value	FAS
F	Incorrect timing			
G	Trial specific violation			
G1	Inclusion criteria violated			
	G1.10	No black/African American or antidiabetic background therapy not as required	Inclusion criterion checked, see individual inclusion criteria	PPS
	G1.11	Blood pressure at screening out of range	Mean seated SBP outside 140-180 mmHg or DBP outside 90-110 mmHg at Visit 1	PPS

Table 6.2: 1 List of important protocol violations (cont.)

PV Category/ Code		Description	(Comments)	Criterion to check for PV	Exclusion from
	G1.12	Use of none or more than 3 antihypertensive medications or use of antihypertensive medications for less than 4 weeks prior to randomization	See inclusion criterion (as specified in the protocol)	I6 ¹ Protocol Version 4 allows 4 antihypertensive treatments, in previous Versions not more than 3 were allowed	PPS
G2	Exclusion criteria violated				
	G2.20	Use of hypertension treatment with oral Minoxidil	See exclusion criteria	E3 ¹	PPS
	G2.21	Blood pressure out of range at placebo run-in confirmed	Mean seated SBP \geq 181 mmHg or mean seated DBP \geq 111 mmHg during placebo run-in visit and confirmed by a 2nd measurement (not on same day) preferably within 1 day	E4 ¹ from Protocol Version 4 onwards SBP criteria only (no DBP criterion)	PPS
	G2.22	Upper arm circumference exceeds cuff size of BP measurement device	Upper arm circumference that exceeds the upper circumference level of the cuff size of either ABPM and/or BP measurement device	E5	PPS
	G2.03	Night shift worker	Night shift workers who routinely sleep during the daytime and/or whose work hours include midnight	E6	PPS

Table 6.2: 1 List of important protocol violations (cont.)

PV Category/ Code		Description	(Comments)	Criterion to check for PV	Exclusion from
	G2.23	Systolic blood pressure difference of >10 mmHg between the arms at screening	See exclusion criteria	E18 (protocol version 1 only)	PPS
G3	Other trial specific violation				
H	Other safety related violations				
H3	Violation of CTP procedure possibly affecting BP measurement				
	H3.01	Incorrect procedure for BP measurement	Not the same arm used for BP measurement for baseline and last value on-treatment	¹	None
	H3.02	Incorrect device used	Incorrect device used for baseline or last value on-treatment	Manual	None
	H3.07	Incorrect sequence for study procedures related to blood pressure	BP measured after blood draw	Manual	None
I	Other safety related violations				
I2	Pregnancy monitoring				
	I2.01	Pregnancy	Pregnancy		None
	I2.02	Missing pregnancy test	Pregnancy test not done for woman of child bearing potential for at least one visit before treatment discontinuation	¹	None

Note: Data check means that the IPV will be manually checked (i.e. derived programmatically)

¹ programming is involved for checking according to project standard

The decision about which PV could generate exclusion from analysis sets will be discussed during the course of the study and finalized at the last blinded report planning meeting (BRPM).

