3.3.2 Inclusion criteria

1. Diagnosis of T2DM prior to informed consent.

Note: Documentation should be available before randomization at latest. Confirmation can be in the form of formal documents or by verbal communication of the date of diagnosis from a patient or from their primary care physician (if records are not available). It is up to the medical judgment of the Investigator to deem if the information is accurate.

2. Male and female black/African American patients on diet and exercise regimen who are EITHER

drug-naïve (defined as absence of any oral antidiabetic therapy, glucagon like peptide-1 (GLP-1) analog or insulin for 12 weeks, 16 weeks for pioglitazone prior to randomisation)

OR

pre-treated with stable dose of

- Metformin only, or
- Sulfonylurea only, or
- DPP-4 inhibitor only, or
- metformin plus sulfonylurea, or

Proprietary confidential information.

© 2016 Boehringer Ingelheim International GmbH or one or more of its affiliated companies. All rights reserved.

This document may not - in full or in part - be passed on, reproduced, published or otherwise used without prior written permission.

- metformin plus DPP-4 inhibitor.

Treatment has to be unchanged for a minimum of 12 weeks prior to randomization.

Dose for metformin: maximum tolerated dose

The maximum daily dose of SU or DPP-4 inhibitor should not exceed that stated in the local label.

3. HbA1c of $\geq 7.0\%$ (53 mmol/mol) and $\leq 11.0\%$ (97 mmol/mol) at Visit 1 (screening).
4. Mean seated SBP 140-180 mmHg at Visit 1 (screening).
5. Successful completion of baseline ABPM testing with a mean SBP 135-175 mmHg prior to randomisation.
6. Treatment with stable doses of at least one but not more than 4 antihypertensive medication ≥ 4 weeks prior to randomisation.
7. Age ≥ 18 years at Visit 1 (screening)
8. Signed and dated written informed consent by date of Visit 1 in accordance with Good Clinical Practice (GCP) and local legislation

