14. Bariatric surgery within the past two years and other gastrointestinal surgeries that induce chronic malabsorption.
15. Medical history of cancer (except for basal cell carcinoma) and/or treatment for cancer within the last 5 years.
16. Blood dyscrasias or any disorders causing hemolysis or unstable Red Blood Cells (e.g. malaria, babesiosis, haemolytic anaemia, thalassemia, sickle cell anaemia (sickle cell trait is allowed)).
17. Medical history and signs and symptoms of diabetic autonomic neuropathy.
18. Treatment with anti-obesity drugs 3 months prior to randomisation (i.e. surgery, aggressive diet regimen, etc.) leading to unstable body weight.
19. Current treatment with systemic steroids at time of informed consent or change in dosage of thyroid hormones within 6 weeks prior to informed consent or any other uncontrolled endocrine disorder except T2DM in the opinion of the investigator.
20. Pre-menopausal women (last menstruation ≤ 1 year prior to informed consent) who:
 - are nursing or pregnant or
 - are of child-bearing potential and are not practicing an acceptable method of birth control, or do not plan to continue using this method throughout the study and do not agree to submit to periodic pregnancy testing during participation in the trial. Acceptable methods of birth control include tubal ligation, transdermal patch, intra uterine devices/systems (IUDs/IUSs), oral, implantable or injectable contraceptives, complete sexual abstinence (if acceptable by local authorities), double barrier method and vasectomised partner.
21. Alcohol, drug or confectionary liquorice abuse within the 3 months prior to informed consent that would interfere with trial participation or any ongoing condition leading to a decreased compliance to study procedures or study drug intake in the investigator's opinion.

Proprietary confidential information.

© 2016 Boehringer Ingelheim International GmbH or one or more of its affiliated companies. All rights reserved.

This document may not - in full or in part - be passed on, reproduced, published or otherwise used without prior written permission.

22. Intake of an investigational drug in another trial within 30 days prior to intake of study medication in this trial; or participating in another trial (involving an investigational drug and/or follow-up) after discontinuing medication in that trial.

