6.3 PATIENT SETS ANALYSED

The following analysis sets will be defined for this trial.

- Screened patients set (SCR): All patients screened for the trial, with informed consent given and who completed at least one screening procedure at Visit 1.
- Randomised set (RS): All patients from the SCR who were randomised to trial drug, regardless of whether any trial drug was taken.
- Treated set (TS): All patients who were randomised and treated with at least one dose of trial drug. The TS is the basis for the safety analyses in the double-blind period.
- Full analysis set (FAS): All patients randomised, treated with at least one dose of trial drug, and with a baseline and at least one on-treatment HbA_{1c} value. The FAS is the basis for the primary efficacy analysis.
- Per-protocol set (PPS): All patients in the FAS without iPVs leading to exclusion. See [Table 6.2: 1](#).

No efficacy or safety analyses are planned for the RS. In [Table 6.3: 1](#) the data sets which are to be used for each category class of endpoint are illustrated.

Table 6.3: 1 Summary of which data sets will be used for which class of endpoints

Class of endpoint	TS	FAS	PPS
Primary		OC OC-AD OC-IR LOCF MI	OC
Key secondary - BP endpoints - Other endpoints		OC-AD (not for ABPM endpoints) OC-H OC-IR LOCF-H OC-AD OC OC-IR LOCF	
Subgroup analyses: - BP endpoints - Other endpoints		LOCF-H OC-H OC	
Binary efficacy endpoints - BP endpoints - Other endpoints		NCF-H NCF	
Other continuous efficacy endpoints - BP endpoints - Other endpoints		OC-H LOCF-H OC LOCF OR#	
Safety endpoints	OR LOCF-IR [^] OC-IR [^]		
Disposition	OR		
Demographics		OR	
Baseline efficacy		OC	

[figure not shown]
Note: LOCF=Last observation carried forward; OC=Observed cases; OR=Original result;

[figure not shown]
MI=multiple imputation

[figure not shown]
Further details of the imputation methods can be found in [Section 6.6](#).

[figure not shown]
#OR results will only be presented for time to first rescue medication and number of patients with rescue.

[^] LOCF-IR and OC-IR will only be used for lipids.

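### The second, free-standing limb of PPS code A3.08 dates anti-obesity drug use from consent and drops the body-weight condition, so it can remove patients who are eligible under exclusion criterion 18

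*SAP*

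**What the plan says.** Protocol 3.3.3, exclusion criterion 18, bars "Treatment with anti-obesity drugs 3 months prior to randomisation (i.e. surgery, aggressive diet regimen, etc.) leading to unstable body weight". It has two elements: a look-back from randomisation, and a consequence for body weight.

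SAP 6.2, Table 6.2: 1, code A3.08, gives two triggers joined by 'or'. The first is that the exclusion criterion is checked. The second is "Treatment with anti-obesity drugs 3 months prior to informed consent or any other treatment at the time of screening", followed by surgery and aggressive dieting as examples. The check column names criterion 18 (19 in protocol version 1). The exclusion column says PPS, without the note reserving the decision for the database-lock meeting that appears on A3.11, C4.01 and D2.01.

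SAP 6.3 defines the PPS as "All patients in the FAS without iPVs leading to exclusion". Protocol 7.3.2 uses it to repeat the primary HbA1c analysis, and SAP Table 6.3: 1 lists it for the primary endpoint only.

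**The concern.** A3.08 is meant to flag breaches of criterion 18, but its second limb states a different rule. It starts the clock at consent and omits the body-weight condition. Because the limbs are alternatives, a patient for whom the site correctly left criterion 18 unticked can still be flagged and lost from the PPS.

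The second limb also stops at consent. If it is there to pick up use that the site did not tick, it does not reach use confined to the weeks just before randomisation. Code D2.01 does not fill that gap, because it concerns "Use of prohibited medication during treatment period".

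At stake is whether the PPS contains the patients it is defined to contain, and so how far it can be read as a check on the primary HbA1c result.

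**Working it through.** The plan states no figure to reproduce. The check compares the two texts and then works out the date windows.

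**Is the difference explained anywhere?** SAP section 4 says the plan follows protocol amendment 4. The visible amendment log shows no change to the anchor in criterion 18. Where a criterion's content changed between versions, Table 6.2: 1 says so (A2.01, G1.12, G2.21); for A3.08 it records only the renumbering. Neighbouring codes keep the protocol's anchors: A3.10 uses consent, as criterion 19 does, and A3.11 uses intake of study medication, as criterion 22 does.

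**Inputs**
- Consent: "Signed and dated written informed consent by date of Visit 1" (Protocol 3.3.2). Assumed here to be at Visit 1.
- Visit 1: Day -21, window +/-7 days; randomisation on Day 1 (Flow Chart). The gap g is taken as 21 days, range 14 to 28.
- 3 months = 91 days (assumption).

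**Windows, in days before randomisation**
- Criterion 18: 0 to 91.
- A3.08, second limb: g to g + 91.
- Flagged by the second limb only: last use from 92 to g + 91, which is g days.
- Inside criterion 18's window but not reached by the second limb: use confined to the last g days.

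| g | Second-limb window | Last use flagged only by A3.08 | Band at each end |
|---|---|---|---|
| 14 | 14 to 105 | 92 to 105 | 14 days |
| 21 | 21 to 112 | 92 to 112 | 21 days |
| 28 | 28 to 119 | 92 to 119 | 28 days |

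**Examples at g = 21**
- Last use 100 days before randomisation: 100 > 91, so outside criterion 18; 21 <= 100 <= 112, so flagged by the second limb. An eligible patient is excluded.
- Use only 10 days before randomisation: 10 <= 91, so inside criterion 18's time window; 10 < 21, so outside the second limb. The first limb catches it if the site ticks the criterion for a patient whose weight became unstable.
- Use 60 days before randomisation with stable weight: inside both windows. Criterion 18 is not met because its weight condition fails, but the second limb still flags the patient.

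The third example does not depend on the anchor. Changing only the date would leave it unresolved.

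**The case against.** The strongest reply is that A3.08 begins with the protocol's own criterion. Its check column points only to that criterion, and the consent wording sits in a comments column. Eligibility is reviewed at Visits 1, 2.1 and 3 (Flow Chart) and again before randomisation (Protocol 6.2.2), so the site can tick criterion 18 for use during run-in. SAP 6.2 also leaves the final choice of excluding violations to the last blinded report planning meeting.

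Much of this stands, and it rules out two readings that a reader might infer. The code as a whole does not count from consent; only its second limb does. Nor does the plan generally miss use during screening and run-in. That use is missed only if it began after consent, ended before treatment, and the site did not tick the criterion. Use that continued into treatment falls under D2.01.

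The reply does not answer the over-exclusion. An unticked criterion gives no protection against a limb that excludes on its own, and the blinded meeting works from this table, where A3.08 carries an unreserved PPS exclusion.

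**Conclusion.** The inconsistency is real and minor. As written, the second limb can remove eligible patients from the PPS: those with last use about 92 to 112 days before randomisation (a 21-day band, range 14 to 28), and those whose use did not destabilise weight. It also does not itself cover use confined to the time between consent and randomisation.

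This rests on 3 months = 91 days, consent at Visit 1 (earlier consent would widen the bands), and reading the weight condition in criterion 18 as applying to the drug treatment.

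A reader might turn 21 of 91 days into a 23% misclassification rate. The documents do not support that: it is a share of calendar days, and no rate of anti-obesity drug use is given. Few patients are likely to be affected; with 77 planned per arm, one patient is 1/77 = 1.3% of an arm. A reader might also infer a threat to the body-weight endpoint or to the confirmatory results. Body weight is not analysed on the PPS, and the primary and key secondary tests all use the FAS.

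**What to change.** Either of two changes to A3.08 would do:

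1. Make the second limb match criterion 18 in both respects: count the 3 months back from randomisation, and require that the use led to unstable body weight.
2. Reduce the trigger to the ticked criterion, plus a data check against criterion 18 as the protocol words it.

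Either removes both mismatched bands and the stable-weight case. Eligibility does not change; the SAP is brought into line with the criterion it cites.

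The cost is one table cell. Programming cost is uncertain, because A3.08 carries neither the data-check wording nor the programming footnote found on A3.06 and A3.09. If a date check has been programmed, its reference date changes. The body-weight condition may need medical judgement at the blinded meeting, since the table gives no rule for deriving it.
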